- Following the Screening Session, eligible participants will be randomized to a treatment group (i.e., SUV or placebo) and protocol arm (i.e., EMG/EEG only or EMG/EEG + fMRI). Treatment group randomization will be double-blinded.
- Research study staff will monitor the participants throughout the course of the research to ensure that they still meet eligibility criteria, and their continuing eligibility will be documented by the research staff. This will include ensuring abstinence from alcohol at both laboratory visits. It will also ensure that no participant is pregnant at either session.
- Upon enrollment into the study, participants will be required to agree and consent to not operating heavy machinery, including driving a vehicle, for at least 24-hours after the Acute Drug Challenge visit due to day-time drug administration.
- Participants will also be instructed that they will be required to fast for at least 2-hours prior to the Acute Drug Challenge visit to avoid interactions between food and SUV metabolism. The Acute Drug Challenge visit will therefore begin at approximately 9-10am.
- Following the Acute Drug Challenge visit, participants will be instructed to take either SUV or placebo, dependent upon their randomized treatment group, once daily before bed for 4 weeks. Participants will complete daily online clinical assessments. The PI and study staff will monitor potential side effects and drug adherence throughout the duration of the 4 weeks.
- Participants will return to the lab at the end of the 4 weeks and complete a third EMG/EEG, and second fMRI (dependent upon randomization).
- Participants will be debriefed and provided AUD treatment referrals as appropriate at the end of their study participation.

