Suvorexant Accountability and Compliance. The compound pharmacy will prepare the study capsules and supply them to OSU Investigational Drug Services (IDS). Appropriate storage temperature of suvorexant will be maintained by IDS. IDS staff will maintain records of distribution to each subject. These records will include dates, quantities, batch, expiration dates, and unique code numbers assigned to the product and study subjects. Prior to distribution, the IDS will prepare each subject's study medication in blister packaging. Each blister is clearly marked with the date the capsule will be ingested.

Administration of Drug or Placebo (Acute Drug Challenge).

Overview. Following the initial EMG/EEG or fMRI visit (dependent upon randomization) participants will return to the lab for the Acute Drug Challenge Visit. Participants will first arrive to the Clinical Research Center (CRC) for drug or placebo administration. After 2-hours, participants will then be escorted to the PI's laboratory for the EMG assessment. After the assessment, participants will return to the CRC for further monitoring and discharge to assure that vital signs (heart rate, oximetry, blood pressure) are within normal limits and/or do not require immediate medical attention and that the participant can maintain wakefulness as demonstrated by a score of 7 or less on the Karolinska Sleepiness Scale (KSS)⁶² (1="Very alert"; 5="Neither alert nor sleepy"; 7="Sleepy, but no difficulty remaining awake; 9="Very sleepy, fighting sleep"). Participants will consent to not operating a vehicle for at least 24 hours after the Acute Drug Challenge Visit. A taxi voucher or Uber reservation will be provided by study staff for transportation home if participants do not have a means to transportation.

Placebo and suvorexant (i.e., Belsomra®; 10mg; Merck & Co., Inc.) will be obtained from the compound pharmacy and will be placed in opaque capsules with dextrose filler for each session. Placebo capsules will be identical in appearance but will contain only dextrose. All capsules will be administered to subjects in double-blind conditions at the CRC under medical supervision.

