Administration Timing. Peak plasma concentration for suvorexant is 2 hours post-ingestion. Therefore, participants will receive the drug (or placebo) at the CRC upon arrival. After 1.5 hours (90 minutes post ingestion), participants will be escorted to the laboratory for EMG/EEG testing. Laboratory assessments will occur during peak concentration, ~2 hours post-ingestion.

Self-Report Assessments During Acute Drug Challenge. Throughout the Acute Drug Challenge Visit standardized questionnaires will be used to assess mood states and subjective drug effects: (1) Karolinska Sleepiness Scale (KSS)⁶²; (2) Anxiety Visual Analog Scales (VAS)⁶³; and (3) Drug Effects Questionnaire (DEQ)⁶⁴; and Profile of Mood

States (POMS)⁶⁵. The KSS, VAS and DEQ will be collected immediately before capsule ingestion (Time 0), and approximately 30, 60, 90, 120, 150, 180, and 210, and 240 minutes afterwards. The POMS will be completed immediately prior to capsule ingestion (Time 0), and approximately 60 minutes, 120 minutes, and 240 minutes afterwards.

Vitals Signs Measurements During Acute Drug Challenge. Physiologic measures will be collected throughout the study visit: (1) Blood Oxygen (O₂) Saturation; (2) Heart Rate and (3) Blood Pressure will be taken before capsule ingestion (Time 0), and approximately 30, 60, 90, 120, 150, 180, and 210, and 240 minutes afterwards. Measurements will be performed at the CRC or in the PI's lab using portable blood pressure and finger oximeter. Measurements will be obtained using a finger oximeter and portable blood pressure cuff. Any participant who experiences excessive drowsiness, allergy symptoms, and/or adverse drug reactions will be assessed by the CRC and study physician and immediately withdrawn from the study as a safety measure.

Drug Trial and Monitoring. At the end of the acute challenge, subjects will be provided the rest of their prescription (SUV or placebo) in blister packaging, prepared by OSU IDS. The blister packaging will be labeled with each date of the protocol. Subjects will be directed to ingest one pill each night, as they get into bed (~30 mins prior to sleep time) to mitigate drowsiness, consistent with SUV's prescription.

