Each morning for the 4-week medication trial period, subjects will be asked to complete a brief clinical assessment, sent directly to subjects' smartphones at 8:30am. The survey will capture: medication adherence (yes/no); timing of pill ingestion; time spent in bed and asleep; medication side-effects; number and timing of alcoholic beverages; alcohol craving; illicit substance use; mood; and new medication usage to monitor potential drug-drug interactions. If the survey is not completed, a reminder will be sent to the participant every 30 minutes for 150 minutes (5 total reminders). Responses will be collected, password-protected, and encrypted locally on smartphones.

Subjects who endorse medication side effects other than nighttime drowsiness will be contacted by the study physician for a review of symptoms and safety. Additionally, if subjects endorse taking new medications, the study physician will review the information and contact the subject if further information is needed. The study physician and PI will utilize Lexicomp to check drug-drug interactions and only interactions of minor severity will be allowed. Those found to have moderate or severe interactions will be withdrawn from the study, consistent with study exclusionary criteria.

Subjects will also be contacted if medication compliance falls below 80% or above 120%. At the final lab visit, subjects will be asked to bring their blister pack with them to verify compliance using the pill count method. Thus, medication compliance is tracked using both daily self-report, pictures, and objective pill count.

Post-Treatment Lab Visits. During the final days of the trial, subjects will return to the lab to repeat the lab protocol. Individuals enrolled in the BRAINS Group will come in for a separate visit to repeat the fMRI. At study conclusion, subjects will be debriefed and provided a list of AUD treatment referrals and resources.

Self-report Data Processing. All measures will be double entered, checked for discrepancies, and cleaned. Analyses will assume that 'missingness' occurred at random, with data imputed when necessary.

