Discovery and disclosure of incidental finding or abnormality on MRI scans: During the formal consent process, all subjects will be informed about the potential risks of discovering an incidental finding or abnormality on their MRI scan. The Center for Cognitive and Behavioral Brain Imaging is a research center. It is NOT a Clinical MRI facility in a hospital. There are no neuroradiologists at the Center for Cognitive and Behavioral Brain Imaging, therefore the staff are unable to make any medical comments on the scans. However, all structural scans obtained in normal research subjects are sent to a neuroradiologist for review. In addition, participants are given the structural images on a CD. In the event the neuroradiologist detects an abnormality, the Center staff will forward his findings to the participant primary care physician (PCP) within one month of the scan. The participant and PCP will receive information that the neuroradiologist has found some abnormalities that could be potentially significant. This will be communicated by a letter. The neuroradiologist will be available to consult with the PCP if it is necessary. Any costs associated with seeing the primary care physician will be participant responsibility. If participants cannot designate a primary care physician in the MRI Screening Form, they cannot participate in the study. Normal scan results will be available one month after the study and will not be communicated to a primary care physician.

Suvorexant-Related Risks: Suvorexant is a Drug Enforcement Administration (DEA) schedule IV-controlled substance in the United States because it is considered to have abuse liability similar to other approved sleep medications (e.g., zolpidem). Preclinical self-administration studies in rats and monkeys indicate suvorexant does not have positive reinforcing effects⁶⁵. In previous clinical trials there has been no evidence of physical dependence with the prolonged use⁶⁶. There is also no evidence of withdrawal or “discontinuation syndrome” following abrupt discontinuation⁶⁶.

Suvorexant is associated with some potential adverse side-effects including: sleepiness or drowsiness, headache, nausea, dizziness, diarrhea, dry mouth, and abnormal dreams. Next day drowsiness is considered the most common side-effect. All

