other side-effects have an incidence between 1-10%. Rare but potentially serious side effects include: worsening of depression and increase of suicidal ideation, complex sleep behavior and sleep paralysis, and temporary weakness in legs. Taking a CNS depressant (e.g., benzodiazepines, opioids, some antidepressants and anxiolytics, other sleeping medication) increase the risk of side effects and should not be taken at the same time as suvorexant. Suvorexant should not be taken with grapefruit juice, as this may significantly increase the levels of medication in the blood. Suvorexant should not be taken unless individuals are able to stay in bed for a full night (at least 7 hours) before they must be active again. Individuals should also not drive, operate heavy machinery, or do other activities that require clear thinking immediately after taking suvorexant.

Co-I, [name], M.D., is a Board-certified psychiatrist and physician, and will be available during the Acute Drug Challenge and Drug Trial in order to evaluate and/or recommend further evaluation and treatment for the emergence of any adverse events/side effects. Participants taking psychoactive/psychotropic medications or medications that would interact with suvorexant will be excluded. Pregnant participants will be excluded from participation because there is insufficient data to assure safety of the fetus during suvorexant exposure. As well, female participants who are not using acceptable methods of contraceptives or abstinence will be excluded. In addition, nursing mothers will be excluded from the study because the extent to which suvorexant is concentrated and excreted in human breast milk is unknown. Participants will be fully debriefed following the study. During debriefing, any questions participants may have will be answered.

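### Withdrawing participants from the study at the acute visit ends drinking follow-up for people already randomised and dosed, so H3a and H3b rest on an untested missing-at-random assumption

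*Combined protocol and SAP*

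**What the plan says.** Randomisation comes straight after screening and before any lab visit: "eligible participants will be randomized to a treatment group" (section 5.0). The acute challenge is the first dose.

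Section 6.0, under vital signs at the acute challenge, states that a participant with excessive drowsiness, allergic symptoms or an adverse drug reaction "will be assessed by the CRC and study physician and immediately withdrawn from the study as a safety measure". No grade or cut-off is attached to the trigger. The sleepiness limit in the overview of the acute challenge, "a score of 7 or less on the Karolinska Sleepiness Scale", is a discharge check and not a definition of the withdrawal trigger.

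The drinking data come later. The morning smartphone survey runs through the 4-week medication period and records "number and timing of alcoholic beverages" (section 6.0, Drug Trial and Monitoring). H3a is analysed from these daily reports (Aim 3, under Statistical Considerations). The only other post-dose drinking measure is the Timeline Follow-back (TLFB) at the post-treatment EMG visit (Appendices, Tables 1 and 2).

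On missing data, section 6.0 (Self-report Data Processing) assumes that missingness "occurred at random, with data imputed when necessary", and section 10.0 repeats this. The Statistical Considerations name no analysis set, imputation model or sensitivity analysis.

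On side-effects, section 7.0 says "Next day drowsiness is considered the most common side-effect".

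**The concern.** The rule removes people from the study rather than from the capsules alone, and safety does not seem to require that. Stopping the drug removes the exposure; a phone survey about drinking adds no drug risk. Section 6.0 already handles side-effects reported at home with contact and review by the study physician, not with automatic removal.

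The people removed are randomised and dosed, and the reason for removal is plausibly caused by the drug. If more are lost on suvorexant, the remaining arms are no longer the randomised arms. The PHDD and DPDD comparison then holds only if the model predicts correctly what the withdrawn people would have drunk. The plan never checks that.

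Drinking is not the key hypothesis; the sample-size paragraph gives that place to startle. However, section 1.0 says the findings are to inform and power a larger trial, so an arm comparison that cannot be checked for this problem has a cost beyond this study.

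**Working it through.** **Step 1: is the loss real on the text?** Setting the provisions in order gives: screening, randomisation, baseline lab visit or visits, first dose at the acute visit, possible withdrawal from the study, 28 daily reports, and the final TLFB. A person withdrawn at the acute visit reaches neither drinking source. That they give no post-dose drinking data is an inference from the withdrawal wording together with the absence of any follow-up provision. Nothing in the document contradicts it.

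**Step 2: is there a figure in the plan to reproduce?** There is none for drinking. The stated 91% power with 40 per arm concerns startle and comes without a numeric effect size, so it does not bear on this point.

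**Step 3: can the number withdrawn be derived?** No. No acute-visit withdrawal rate is given. The 10 mg pilot is described as free of adverse reactions (section 6.0, Randomization, Blinding, and Dosing), without a sample size. The percentage range in section 7.0, "other side-effects have an incidence between 1-10" per cent, covers effects other than next-day drowsiness, so it is not a rate for a trigger that lists drowsiness first.

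**Step 4: size by illustration.** Let k be the number of 40 suvorexant participants without drinking data, with none lost on placebo. Let d be their actual PHDD minus what the model fills in.

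- Shift in the arm contrast = (k/40) × d
- Standard error of the contrast = SD × √(2/40)

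The plan gives none of k, d or SD; all three are assumed.

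| k | d (points) | SD (points) | Shift (points) | SE (points) | Shift/SE |
|---|---|---|---|---|---|
| 0 | any | any | 0 | – | 0 |
| 2 | 10 | 35 | 0.5 | 7.8 | 0.06 |
| 2 | 20 | 30 | 1.0 | 6.7 | 0.15 |
| 4 | 30 | 25 | 3.0 | 5.6 | 0.54 |

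For the third row: (2/40) × 20 = 1.0; 30 × √0.05 = 6.7; 1.0/6.7 = 0.15. The sign of the shift follows the sign of d, which is unknown. Equal loss of similar people in both arms largely cancels.

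**Step 5: what the shift contains.** Withdrawn people are off drug. Suppose suvorexant changes PHDD by δ on drug and has no effect off drug, and the model fills in on-drug values correctly. Then the size of d equals the size of δ although missing at random holds exactly for the on-drug question. The shift is (2/40) × δ = 0.05δ, which is the same quantity as the dilution of the assignment effect to 1 − 2/40 = 0.95 of the on-drug effect. So the step 4 figures cannot be read wholly as failure of the missing-at-random assumption.

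**Step 6: precision.** For k = 2 the SE grows by a factor √[(1/38 + 1/40)/(2/40)] = 1.013. Loss of precision is not the issue.

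**The case against.** The strongest reply is that the effect is small and its existence uncertain. If nobody is withdrawn it is zero, and the pilot gives some reason to expect few withdrawals. Even two losses with a 20-point gap move the contrast by about 0.15 SE, on outcomes that are not the key hypothesis. This stands, and it limits the point to a modest improvement.

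A second reply is that H3a asks about daily suvorexant, and someone stopped at the first dose never starts daily use. A sponsor may legitimately want the on-drug effect. This also stands in part: it is why step 5 separates the two questions and why an on-drug analysis belongs beside the analysis by assigned arm. It does not remove the need to know how the withdrawn people drank when arms are compared as randomised.

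A third reply is that sleepiness, mood and vital signs are measured repeatedly after the dose and could support imputation. They could, and because the trigger has no cut-off, some retained participants may resemble those withdrawn. But no model that uses these measures is described.

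A fourth reply is that approval for 120 participants covers withdrawals. It restores numbers, not comparability.

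Three stronger readings are tempting and not supported. A reader might infer from the 1 to 10 per cent range that 0.4 to 4 of 40 suvorexant participants would be lost; that range excludes next-day drowsiness and is not a rate for this rule. A reader might take the 0.54 SE row as the expected bias; it is an assumed corner in which every input is unfavourable. A reader might conclude that the result is biased towards suvorexant; the documents fix no direction.

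**Conclusion.** The concern holds for H3a and H3b. A stated rule, not a missing detail, ends drinking follow-up for randomised, dosed participants for a reason that may be drug-related, and nothing in the plan tests the assumption that then carries the comparison by assigned arm. Only the mechanism is established. The size and direction are unknown, and the illustration of 1 point (about 0.15 SE) depends wholly on the assumed k = 2 on suvorexant, none on placebo, d = 20 and SD = 30. Part of any such shift may be the difference between the effect of assignment and the on-drug effect. The change is worth making because it costs little, not because a large bias has been shown. It does not reach H3c, which needs post-treatment reactivity, and it recovers no startle data for Aims 1 and 2.

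**What to change.** - In the acute-challenge text of section 6.0, replace withdrawal from the study with stopping capsules and lab tasks. Leave the safety assessment unchanged.
- Unless consent is withdrawn, continue the existing daily survey to day 28 and take the final TLFB by phone. Apply the same to participants removed for drug interactions under Drug Trial and Monitoring.
- Analyse PHDD and DPDD for all randomised participants in their assigned arm, using all reports, and label this the effect of assignment. Keep an on-drug analysis as supporting.
- Report the number withdrawn, by arm.
- Add one sensitivity analysis that sets remaining missing days to the participant's own baseline drinking, from the past-3-month TLFB at Lab Visit 1. This also covers missing days from other causes, such as the termination criteria in section 5.0.

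The cost is a small change to protocol, consent and analysis wording, and a few extra surveys and calls; no new procedure is needed. The downside is slight dilution relative to the on-drug effect, for example to 0.95 of it with two of 40 off drug, if there is no effect off drug.

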Drug-Alcohol Interactions: To date, there have been at least three human laboratory studies that have directly investigated the pharmacokinetic (PK) and pharmacodynamic (PD) interactions between ethanol and orexin antagonists⁶⁷⁻⁶⁹. All three studies used the highest possible dose of orexin-based medication to robustly probe for the potential for ethanol interactions (e.g., 40mg of suvorexant). All three studies confirmed that coadministration with ethanol does not alter the PK of orexin therapeutics, apart from potentially prolonging time to reach maximum plasma concentration (t_{max}) by about 75 mins. There is no effect of orexin therapeutics on the ethanol concentration versus time profile. With regard to PD, co-administration produced additive impairment on measures of sustained attention/vigilance, balance, and working memory. There was no evidence of supra-additive effects. High doses of orexin antagonism alone, and in combination with ethanol, were well tolerated with no severe or serious AEs reported and no observed effects on clinical laboratory or cardiac variables. Mild to moderate treatment emergent adverse events (TEAEs) reported following co-administration included headache, fatigue, and sudden onset of sleep. There was no impact of co-administration on positive or negative mood. All three studies concluded that concomitant use of alcohol and orexin-based antagonists should be avoided due to the potential for additive psychomotor effects; though there are no serious concerns regarding safety and tolerability like with other sleep medications such as hypnotics. Participants will be informed of these risks during informed consent and at the Acute Drug Challenge Visit.

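### The home dosing direction leaves out the protocol's own condition of at least 7 hours in bed

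*Combined protocol and SAP*

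**What the plan says.** The home dosing direction is in section 6.0, under Drug Trial and Monitoring: "Subjects will be directed to ingest one pill each night, as they get into bed". The same sentence adds that this agrees with the drug's prescription. Section 5.0 also prescribes a single bedtime dose each day for 4 weeks. Neither place sets a minimum time in bed or says when a dose should be left out.

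The condition appears only in the risk text. Section 7.0, under Suvorexant-Related Risks, states: "Suvorexant should not be taken unless individuals are able to stay in bed for a full night (at least 7 hours") before they have to be active again.

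Three other parts of section 6.0 bear on the point:

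- The morning survey records "medication adherence (yes/no); timing of pill ingestion; time spent in bed and asleep; medication side-effects; number and timing of alcoholic beverages", along with craving, mood and other items.
- The contact rules are "Subjects who endorse medication side effects other than nighttime drowsiness will be contacted by the study physician for a review of symptoms and safety", a review of any new medication, and "Subjects will also be contacted if medication compliance falls below 80% or above 120" per cent.
- The BEHAVIOR Group Overview expects the post-treatment assessment to follow a dose taken the night before.

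Section 4.2 excludes people who work night shifts.

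**The concern.** A participant who gets into bed late and must rise early meets two statements that cannot both be followed. The direction says to take the capsule. The risk section says the drug is not for that night. The participant acts on the direction, and the rest of the home procedure points the same way: each blister carries the date on which its capsule is due, and low compliance leads to a call.

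What is at stake is next-day impairment after a short night. Section 7.0 names next-day drowsiness as the commonest side effect. Only the suvorexant arm (40 of the planned 80) is exposed to it, although under blinding both arms receive the same instruction. This concerns participant safety and the protocol's consistency with itself. It does not touch the analysis.

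**Working it through.** The plan gives no figure on this point to reproduce, and the stated 91% power plays no part. The check is a comparison of texts, followed by short arithmetic on the cost of the remedy.

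**Step 1. The two instructions side by side.**

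- On a night with 7 hours or more available, sections 5.0 and 6.0 say take the capsule and section 7.0 permits it. There is no conflict.
- On a night with fewer than 7 hours available, sections 5.0 and 6.0 still say take it, and section 7.0 says it should not be taken.

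Section 7.0 states a condition and no skip rule, so planning a long enough night also satisfies it. Once a short night is unavoidable, however, leaving the capsule out is the only way to comply.

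**Step 2. Does another rule catch the short night?** Time in bed is recorded, but the next morning, after the dose. The contact rules act on side effects, new medications and compliance. None acts on time in bed. Next-day drowsiness would lead to physician contact under the side-effect rule, because it is not the exempted nighttime kind. That is a response to harm and does not prevent it.

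**Step 3. Exposure lost if capsules are skipped.** Input: 4 weeks x 7 nights = 28 home capsules. Share taken after k skips = (28 - k)/28, assuming every other capsule is taken.

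- k = 1: 27/28 = 96.4%, a loss of 1/28 = 3.6%
- k = 5: 23/28 = 82.1%
- k = 6: 22/28 = 78.6%

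The 80% line falls at 0.80 x 28 = 22.4 capsules, so over the full period the sixth skip crosses it. The written consequence is a contact. The compliance rule itself does not call for withdrawal or exclusion from analysis.

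**Step 4. How many nights are affected?** The planned active capsule-nights number 40 x 28 = 1,120. The documents give no distribution of time in bed for this population, so the share with under 7 hours cannot be derived and no estimate is offered.

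**Step 5. The night before testing.** A skip on that night would break the expectation of a dose the previous evening, so the remedy has to protect that night.

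**Step 6. Can a skip be told apart from non-adherence?** The listed survey items give adherence as yes or no, pill timing and time in bed. No item asks why a dose was missed. Actual time in bed is not the time expected when the decision was made, and a pill count cannot supply the reason either.

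**The case against.** The strongest reply is that the condition is already in the protocol and only its place is at issue. The direction says it agrees with the prescription, which can be read as bringing in the conditions of use. Section 13.1 says the consent document covers the drug's risks, and the consent pages are not available here, so what participants are told about 7 hours cannot be checked. Night-shift workers are excluded, 10 mg is the lowest clinical dose, and the first dose is supervised, with withdrawal for excessive drowsiness. Section 5.0 adds: "The PI and study staff will monitor potential side effects and drug adherence throughout the duration of the 4 weeks". All of this stands, and it makes the remaining risk small. It does not make the written direction agree with section 7.0. The point can be held only against that written direction, and not against everything participants hear.

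A reader might infer something stronger from the side-effect contact rule: that exempting nighttime drowsiness leaves a hole on nights with both a capsule and alcohol. Entry requires heavy drinking, and section 7.0 reports the conclusion of three laboratory studies that "concomitant use of alcohol and orexin-based antagonists should be avoided due to the potential for additive psychomotor effects". The documents do not support treating the exemption as a defect, for four reasons:

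- Drowsiness at night is the expected effect of a sleep drug taken at bedtime.
- Every other side effect already leads to contact, including the headache, fatigue and sudden sleep onset reported after co-administration.
- The hazard described is co-use itself. A trigger that depends on reported drowsiness would miss co-use without that complaint.
- Section 7.0 reports no supra-additive effect and no severe or serious events at high doses (40 mg of suvorexant, for example). It also says "Participants will be informed of these risks during informed consent and at the Acute Drug Challenge Visit".

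A further trigger would be a preference about how intensively to monitor. Nor do the documents give a rate from which to count drowsiness-only reports on drinking nights.

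**Conclusion.** The point holds as a minor safety matter with a cheap remedy. Two dosing directions omit a condition that the protocol itself sets, and on a short night, following them breaks it. The conclusion rests on the written protocol alone and assumes that no unseen participant material already states the 7-hour condition. If such material does, the change only brings the protocol into line with it.

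The frequency of short nights, and so the number of affected doses, is unknown.

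Two further inferences should be resisted. One is that participants who skip correctly are penalised; they are at most contacted, and that conversation could itself bring short nights to light. The other is that the randomised comparison is biased. The direction is the same in both arms, and nothing in the documents shows such an effect.

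**What to change.** In section 6.0, Drug Trial and Monitoring, after the phrase about getting into bed, add: *only if at least 7 hours remain in bed; otherwise skip that night's capsule*. Make the dosing bullet in section 5.0 refer to it.

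Ask participants to keep at least 7 hours free on the night before a post-treatment visit, so that the planned dose on the previous night can be taken.

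If the team wants to separate these skips from non-adherence, add one item to the morning survey asking why a dose was missed. The below-80% rule can stay as written.

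The cost is one clause, one reminder before the visit and, optionally, one survey item. The downside is the 3.6% of planned home exposure lost with each skipped capsule. Section 7.0 already implies that loss whenever a short night cannot be avoided.
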